## 11.3 Technical Malfunctions of the Pre-filled Injection Pen

The frequency of technical malfunctions of the administration pen will be tabulated and all technical malfunctions will be listed.

## 12 Post-trial Information

Live birth rate and neonatal health, including minor / major congenital anomalies, at birth and at 4 weeks after birth will be described. These data will be reported separately. Live birth and live at 4 weeks status will be analysed using the same method as for pregnancy endpoints.

---

 An adverse reaction is defined as an adverse event with reasonable possible causal relationship to IMP

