## 7.4 Assessments related to Post-trial Information

### 7.4.1 Pregnancy Follow-up

For subjects with an ongoing pregnancy in the fresh cycle, information on the pregnancy period, including any relevant interventions performed and incidence of second or third trimester losses, as well as the pregnancy outcome, e.g. live birth, will be gathered. Further, neonatal health data will be collected at birth and at 4 weeks after birth for all children born. At birth, the data collected will include gender, birth weight and length, type of delivery, fetal presentation and apgar score as well as information on minor/major congenital anomalies and admission to neonatal intensive care unit (NICU)/pediatric intensive care unit (PICU) or neonatal care unit (NCU)/pediatric care unit (PCU). At 4 weeks after birth, the data collected will include minor/major congenital anomalies, hospitalisations and any other relevant medical conditions. These follow-up data can be obtained from the subject, unless medical judgement is required, and will be reported separately.

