### Informed Consent regarding Data Collection on the Neonate – Child-custody Holders

For countries where a separate information and informed consent form is required to collect pregnancy outcome data on the neonate, the investigator will obtain a freely given written consent from the child-custody holders, i.e. the subject and the subject's partner in case of joint custody. The child-custody holders must be given ample time before the consent is obtained. The Informed Consent Form must be signed and dated by the child-custody holders and the investigator who has provided information to the child-custody holders. Written consent by the child-custody holders regarding collection of pregnancy outcome data on the neonate must be obtained before the subject is randomised and preferably at the time of obtaining written consent by the subject regarding participation in the trial.

The investigator will explain that the child-custody holders are completely free to refuse to consent to this data collection or to withdraw consent at any time, without any consequences and without the need to justify their decision.

The child-custody holders will receive a copy of the Informed Consent Form.

The child-custody holders will be informed that the monitor(s), quality assurance auditor(s) mandated by Ferring, ethics committee representatives or regulatory authority inspector(s), in accordance with applicable regulatory requirements, may review the neonate's source records and data. Data protection will be handled in compliance with national / local regulations.

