## 10 Efficacy

### 10.1 General Considerations

The primary objective of the trial is to evaluate the effect of individualised FE 999049 treatment on ovarian response in a long GnRH agonist protocol versus a GnRH antagonist protocol. The primary endpoint is the number of oocytes retrieved.

The estimand of interest is the difference between FE 999049 treatment in the long GnRH agonist protocol versus treatment with FE 999049 in the GnRH antagonist protocol for all randomised subjects, assuming that all subjects start treatment with FE 999049. In the statistical analyses, subjects that discontinue after randomisation but before start of FE 999049 treatment (except for subjects that never started treatment due to the COVID-19 pandemic, which are not included in any analysis) will have their endpoint data imputed from subjects who started FE 999049 treatment in the same protocol, using a multiple imputation method. No imputation will be done for subjects who discontinue the trial after starting FE 999049 treatment. For these subjects, the actual data will be used and not be regarded as missing. Therefore, the number of oocytes retrieved will be regarded as zero and pregnancy outcomes will be regarded as negative.

The trial is descriptive and no formal hypothesis will be tested. The statistical analyses aims at estimating any potential differences between FE 999049 treatment when applied in the two different GnRH protocols. The results will generally be described as an estimated mean treatment difference or treatment ratio and an associated 95% confidence interval.

Since the trial is descriptive without any hypothesis testing, no corrections for multiplicity will be applied.

Analyses and descriptions for ovarian response endpoints and other pharmacodynamics endpoints will be based on the FAS. Analyses and descriptions for pregnancy endpoints will be based on the FAS but excluding subjects that had transfer cancellation due to the COVID-19 pandemic.

Additional descriptions for pregnancy endpoints will be made based on the FAS (i.e. including also the subjects with transfer cancellation due to the COVID-19 pandemic). Analyses and descriptions of safety endpoints and exposure will be based on the safety analysis set.

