## **Pregnancy Rates**

The percentage of subjects with positive  $\beta$ hCG, clinical pregnancy, vital pregnancy, and ongoing pregnancy will be described for each of the two protocols and for subgroups based on age strata and AMH. Pregnancy rates will be compared between the long GnRH agonist protocol and the GnRH antagonist protocol using a logistic regression model with treatment (long GnRH agonist or GnRH antagonist), age stratum ( $<35$ , 35-37, or 38-40 years), and AMH at screening ( $<15$  pmol/L or  $\geq 15$  pmol/L) as factors. The results of this analysis (in terms of odds for pregnancy) will be converted into proportions, differences in proportions, and 95% CIs for differences in proportions using the delta method.

To account for subjects withdrawing from the trial before starting FE 999049 treatment, the multiple imputation method applied for the primary endpoint will be used, using a logistic regression model instead of a negative binomial regression model. Pregnancy data for subjects with pregnancies occurring before start of FE 999049 treatment will not be included in the analysis. These subjects are withdrawn and their data will be imputed.

Missing pregnancy assessments will be assumed to indicate a negative test. If, however, a subsequent test is positive, a previous missing assessment will be considered as positive (if e.g. the clinical pregnancy assessment is missing but the ongoing pregnancy assessment is positive, the missing clinical pregnancy assessment will be regarded as positive).

The main analyses of pregnancy rates will be based on subjects in the FAS, but excluding subjects that had transfer cancellation due to the COVID-19 pandemic. Additional analyses will be made for the FAS, and also for subjects in the FAS that started treatment with FE 999049, i.e. without using multiple imputations (i.e. the safety analysis set).

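### SAP 12 applies the pregnancy rule (missing = negative) to 4-week status, so a subject with a documented live birth but no 4-week report counts as having no live infant at 4 weeks

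*SAP*

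**What the plan says.** SAP 12 first says that live birth and neonatal health will be described and reported separately. It then adds: "Live birth and live at 4 weeks status will be analysed using the same method as for pregnancy endpoints". No rule for missing post-trial data follows.

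The method referred to is in SAP 10.3, Pregnancy Rates. It has three parts:

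- A logistic regression on treatment, age stratum and AMH group.
- Multiple imputation with a limited purpose: "To account for subjects withdrawing from the trial before starting FE 999049 treatment, the multiple imputation method applied for the primary endpoint will be used".
- A rule for gaps: "Missing pregnancy assessments will be assumed to indicate a negative test". The one exception works backwards in time: "If, however, a subsequent test is positive, a previous missing assessment will be considered as positive".

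SAP 10.1 is consistent with this: "No imputation will be done for subjects who discontinue the trial after starting FE 999049 treatment". Pregnancy outcomes for such subjects are taken as negative.

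Protocol 9.6.3 has the same rule for missing pregnancy assessments. For post-trial information it plans description only, so it supplies no alternative rule for 4-week status.

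On collection, protocol 7.4.1 says: "Further, neonatal health data will be collected at birth and at 4 weeks after birth for all children born". It also says: "These follow-up data can be obtained from the subject, unless medical judgement is required". No later assessment of infant status is planned.

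**The concern.** Missing = negative is a familiar and defensible convention for a woman who stops before a pregnancy test. It does not carry over well to the status of an infant already recorded as born alive. There it turns an absent report into an adverse status, although the last known fact was favourable.

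Some missing 4-week reports are foreseeable. The information is gathered after the subject's last trial visit and may come from the subject herself. Where a separate neonatal consent is used, the custody holders are "completely free to refuse to consent to this data collection or to withdraw consent at any time".

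Protocol 3.5.2 says the neonatal data are gathered as additional safety information. At stake is whether the gap between the live-birth rate and the live-at-4-weeks rate can be read as infant loss, or whether it mixes deaths with lost reports.

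**Working it through.** **The plan's own figures.** The documents give no live-birth rate, no expected loss of 4-week reports and no precision target for this outcome. The only design figure is the half-width for the oocyte difference (SAP 4.2): 1.96 × 7.0 × √(2/200) = 1.37, stated as 1.4. It reproduces and has no bearing here.

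**Tracing the rule.** Take a treated subject with a recorded live birth and no 4-week report.

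1. SAP 12 sends 4-week status to the pregnancy method.
2. Multiple imputation does not apply, because she started FE 999049.
3. The missing assessment is therefore scored negative.
4. The exception needs a later positive assessment, and none is planned after 4 weeks.
5. Nothing in the method carries an earlier positive forward.

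Result: live birth = yes, live at 4 weeks = no, with no death recorded. In the reverse case, with the birth record missing and a live infant reported at 4 weeks, live birth is filled in as positive. The unit throughout is the subject; handling of twins is not stated.

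**Illustrative size.** Inputs:

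- n = 200 per arm (SAP 4.2).
- p, the share of subjects with a live birth: assumed 25% to 30.7%. The upper value is the ESTHER-1 ongoing pregnancy rate for FE 999049 (protocol 1.1). This gives 50 to 61.4 subjects per arm.
- m, the share of those with no 4-week report: assumed 2% to 10%.
- No true infant death.

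Misclassified per arm = n × p × m. Reported 4-week rate = p × (1 − m).

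| m | Misclassified per arm | Reported rate, p = 25% | Reported rate, p = 30.7% |
|---|---|---|---|
| 2% | 1.0 to 1.2 | 24.5% | 30.1% |
| 5% | 2.5 to 3.1 | 23.8% | 29.2% |
| 10% | 5.0 to 6.1 | 22.5% | 27.6% |

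At m = 5%, survival among live births would read 95% with no death.

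**Difference between arms.** With 0% missing in one arm and 10% in the other, the spurious difference is p × 0.10 = 2.5 to 3.1 percentage points. The 95% CI half-width, 1.96 × √(2p(1 − p)/200), is 8.5 points at p = 25% and 9.0 at p = 30.7%.

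**Would dropping unknowns cure it?** Not in a model of all subjects. Women without a live birth have a known negative status, so those dropped are mainly positives. With p = 30.7%, m = 10% and all unknowns truly positive, the rate among known status is 0.307 × 0.90 / (1 − 0.307 × 0.10) = 0.2763/0.9693 = 28.5%. That is still 2.2 points below 30.7%, against 3.1 points under missing = negative.

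**The case against.** **The cross-reference may mean only the model.** SAP 10.3 speaks of pregnancy assessments and a negative test, and infant status is neither. That reading is possible. But the SAP would then have no rule at all for a missing 4-week report, and section 12 would still need one.

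**Deaths are captured elsewhere.** A reader might infer that the plan will produce a false neonatal mortality signal. The documents do not support going that far. Protocol 8.5.1 makes stillbirth and death of a neonate or infant serious adverse events, and both checklists in protocol 14.7 ask about neonatal death. Mortality would not be judged from the difference of two rates alone. What stands is narrower: the analysed 4-week result could contradict that safety record.

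**Missing reports may be few.** The consent provision in protocol 14.5 applies only where a separate form is required. Consent must then be obtained before randomisation, so refusal should surface before entry and later withdrawal is the relevant route. Protocol 10.1 requires 4-week neonatal health in the source documents, and protocol 11.1 checks entries against physicians' reports, the subject's own information or other sources. All of this stands, and the loss rates above are assumptions.

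**Live birth is not affected in the same way.** A reader might extend the point to live birth. There a live infant reported at 4 weeks fills in the missing birth record, and missing = negative is otherwise a defensible convention.

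**A treatment-effect artefact is unlikely to be visible.** Even 0% against 10% missing gives a difference well inside the confidence interval, in a trial with no hypothesis testing.

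**Conclusion.** The point holds for 4-week status. Followed as written, SAP 12 and SAP 10.3 count a subject with a documented live birth and no 4-week report as having no live infant at 4 weeks. The harm is a false gap between live birth and 4-week status, more than a false difference between the arms.

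On the assumptions shown (25% to 30.7% with a live birth, 5% of those without a 4-week report), about 2.5 to 3 subjects per arm would be misclassified. With complete reporting the effect is zero. It is confined to a post-trial outcome reported separately and leaves the primary endpoint untouched. The correction is cheap and should be made before the post-trial data are analysed.

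**What to change.** In SAP 12:

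- Exempt 4-week status from the missing = negative rule. For a subject with a documented live birth, score not live at 4 weeks only if a neonatal death is documented. Otherwise carry the live-birth status forward in the all-subject model.
- Show by arm the number of live births with unknown 4-week status and the number of ongoing pregnancies with unknown birth outcome.
- Report missing = not alive as a worst-case sensitivity result.
- Describe 4-week survival among live births with known status.
- Do not restrict the all-subject model to known status, since that drops mainly positives.

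The missing = negative rule for live birth itself may stay, with the unknown count shown.

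The cost is a few sentences, the two counts and one sensitivity result. No new data are needed. The small downside is that carrying forward assumes no unreported death; the worst-case result bounds that.

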### 13 Interim analyses

No interim analysis is planned.

### 14 Changes to the analyses described in the protocol

This SAP does not introduce any changes to the analyses already described in the trial protocol. A few additional details and clarifications have been added, and a few additional analyses have been added. These include the following:

- Addition of supplementary analyses based on subjects in the FAS starting treatment with FE 999049, i.e. analyses without the use of multiple imputations (this is the same as using the safety analysis set).
- Clarification that the analysis of number of MII oocytes will be based on subjects that had all their oocytes inseminated using ICSI, and subsequently multiple imputations will not be used.
- Addition of analyses for number of follicles, embryos, number of good-quality embryos, and number of blastocysts.
- Addition of analyses for number of stimulation days, total dose, and the average daily dose of FE 999049 treatment.
